renal function maturation (Rhodin 2009) on ORGN001 PK in neonate patients. [REDACTED]

Dosing will be based upon the gestational age (GA) of the patient. [REDACTED]

[REDACTED] Following Investigator and Safety Review Committee (SRC) reviews (as well as Data Monitoring Committee [DMC] review of data prior to the first dose adjustment for each patient as well as subsequent periodic review of cumulative data); recommended dosing may follow the guidance in [Table 3](#).

The dosing strategy in [Table 3](#) has been simplified compared to the original guidance. This is justified given 1) the much greater safety margin with respect to the NOAEL described above; 2) the excellent safety profile of ORGN001 thus far with all patients tolerating the maximum 1200 µg/kg dose well and no safety signals identified [REDACTED]; and 3) the fact that dose increments [REDACTED] were well tolerated in Study ALXN1101-MCD-201.

Table 3: Dosing and Dose Adjustment for Term and Preterm Neonate Patients, Older Infants, and Children in Study ALXN1101-MCD-202

Study Day	Term Neonate (GA \geq 37 weeks) and Older Infants/Children Dose (µg/kg/day)	Preterm Neonate (GA $<$ 37 weeks) Dose (µg/kg/day)
Day 1	700	525
Day 28	1000	900
Month 3	1200	1200

Abbreviations: GA=gestational age.

Doses may be adjusted based on drug-related AEs or changes in clinical parameters, laboratory data, or PK findings and will occur following consultation with the medical monitor and, if applicable, with the SRC.

Day 1 PK samples will be analyzed, and PK assessments will be completed for a DMC meeting that will be scheduled prior to the first dose adjustment. If the Day 1 AUC is greater than the upper of the target AUC range [REDACTED], there will be a dose recommendation for a decrease by the percentage that the individual AUC is greater than the midpoint of the target AUC range [REDACTED].

If the Day 1 AUC is less than the lower limit of the target AUC range [REDACTED], there will be a dose recommendation for an increase by the percentage that the individual AUC is less than the midpoint of the target AUC range [REDACTED].

Number of patients (planned):

There will be no minimum or maximum number of patients for this study.

Diagnosis and main criteria for inclusion

Inclusion criteria:

Patients must meet all of the following inclusion criteria to be considered for enrollment in this study:

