2.5. Rationale for Proposed Dosing

A population PK (PopPK)-based approach has been utilized to create a dosing scheme that targets the higher end of the originally acceptable exposure range for ORGN001 (NOAEL: area under the plasma concentration-time curve [REDACTED]) at the highest dose studied in the original toxicology study that was limited by solubility issues. Since then, higher doses have been studied and were all well tolerated in rats and dogs using an improved IV formulation. Accordingly, the revised NOAEL values in a [REDACTED] rat study provide a considerable increase in the safety margins [REDACTED].

A PopPK model was derived to characterize ORGN001 clinical PK in healthy adult volunteers (Study ALXN1101-MCD-101) and children with MoCD Type A (Study ALXN1101-MCD-201). Due to [REDACTED] renal clearance of ORGN001 in adults (Study ALXN1101-MCD-101), a function was included to account for the expected impact of renal function maturation ([Rhodin 2009](#)) on ORGN001 PK in neonate patients. [REDACTED]

Dosing will be based upon the gestational age (GA) of the patient. Day 1 dosing for term (≥ 37 weeks GA) and preterm neonate (< 37 weeks GA) patients will begin with ORGN001 IV infusions of 700 and 525 $\mu\text{g}/\text{kg}/\text{day}$, respectively. Following Investigator and Safety Review Committee (SRC) reviews (as well as Data Monitoring Committee [DMC] review of data prior to the first dose adjustment for each patient as well as subsequent periodic review of cumulative data), recommended dosing may follow the guidance in [Table 9](#).

The dosing strategy in Table 9 has been simplified compared to the original guidance. This is justified given 1) the much greater safety margin with respect to the NOAEL in the [REDACTED] rat

study described above; 2) the excellent safety profile of ORGN001 thus far with all patients tolerating the maximum 1200 µg/kg/day dose and no safety signals identified [REDACTED]

[REDACTED]; and 3) the fact that dose increments [REDACTED] were well tolerated in Study ALXN1101-MCD-201.

Table 9: Dosing and Dose Adjustment for Term and Preterm Neonate Patients, Older Infants, and Children in Study ALXN1101-MCD-202

Study Day	Term Neonate (GA ≥ 37 weeks) and Older Infants/Children Dose (µg/kg/day)	Preterm Neonate (GA < 37 weeks) Dose (µg/kg/day)
Day 1	700	525
Day 28	1000	900
Month 3	1200	1200

Abbreviations: GA = gestational age.

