Doses may be adjusted based on drug-related AEs or changes in clinical parameters, laboratory data, or PK findings and will occur following consultation with the medical monitor and, if applicable, with the SRC.

[REDACTED]
ORGN001 drug product has been developed for IV use. Administration via the parenteral route results in rapid and consistent onset of action necessary for treatment of neonatal patients with MoCD. The dose can be adapted to the last recorded body weight or body weights recorded by the home care giver and/or physician visits with appropriate documentation; the flexibility to adjust doses based on changes in body weight enable accurate dosing.

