5. SCHEDULES OF ASSESSMENTS

The detailed Schedule of Assessments for the initial 12-month Treatment Period and the Schedule for the long-term Treatment Period are provided [REDACTED] [REDACTED].

Table 10: Schedule of Assessments (Screening/Baseline and 12-Month Study Period)

Assessment	Screening / Baseline	12-Month Study Period
Study Day		
Month		
Visit Window (Days)		
Informed consent		
Eligibility		
Demographic data		
Genotype		
Family history		
Medical history		
Physical examination ^b		
Vital signs ^b		
Vital status		
Additional BP measurements ^c		
Chemistry and Hematology ^{b,d}		
Urinalysis ^{b,e}		
Growth parameters		
Feeding pattern		
Neurologic examination ^b		
Modified Glasgow Coma Scale		
Bayley-III (or WPPSI-IV) ^f		
GMFM-88 ^g		
GMFCS-E&R		
PEDI ^h		
Ophthalmologic examination		
Seizure activity ^{b,i}		

Assessment	Screening / Baseline	12-Month Study Period	
Study Day			
Month			
Visit Window (Days)			
Brain MRI ^j			
Brain ultrasound ^k (neonates only)			
ECG ^{b,l}			
EEG ^m			
PD sampling, urine			
PD sampling, blood ^{b,n}			
PK sampling ^{b,o}			
[REDACTED]			
ORGN001 infusion ^p		Daily	
Concomitant medications/procedures ^b	X	Continuous monitoring	
Assess AEs ^b		Continuous monitoring	
Follow-up Visits			

Note regarding blood samples: The total blood volume will not exceed the amount considered acceptable for the patient's clinical condition and the institution's guidelines [REDACTED]. If an Investigator decides to deviate from these limits, the deviation must be fully documented and the Investigator should provide justification for the deviation.

With agreement from the Sponsor, some Baseline assessments may be completed after dosing has begun due to urgency of study drug initiation.

^a For neonate patients born prior to 37 weeks of gestation, the Month 12 assessments will be performed at target time point, adjusted for prematurity by scheduling the visit date plus the addition of the difference between gestational age and full-term gestation of 40 weeks.

^b These assessments will be performed when any dose adjustment occurs: physical examination, vital signs, neurologic examination, ECG, PD sampling (blood), PK sampling, serum chemistry, hematology, urinalysis, evaluation for seizure activity, assessment of concomitant medications, assessment of AEs. Electrocardiograms should be performed prior to any blood draws or treatment administration scheduled for the same study visits.

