6. SAFETY REVIEW COMMITTEE AND DATA MONITORING COMMITTEE

6.1. Safety Review Committee

To monitor patient safety, data will be reviewed regularly by the Investigator or designee throughout the study. [REDACTED]

[REDACTED] The SRC will review [REDACTED] data for each individual at the following time points:

- [REDACTED] in advance of the first dose adjustment [REDACTED]
- At any other time during the study, as requested by the Investigator or Sponsor, [REDACTED]

Note that the DMC also will review each patient's record [REDACTED], prior to any study dose escalation [REDACTED]. Further information on the DMC is available in [Section 6.2](#).

[REDACTED] Based on SRC review of the available data, [REDACTED]

the SRC may recommend stopping, increasing, decreasing, or maintaining (current dose) the dose of ORGN001.

The Investigator or Sponsor may also convene the SRC for unscheduled dose adjustments, based on drug-related AEs or changes in clinical parameters.

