6.1.2. Criteria for Adjustment or Stopping Doses

The following are examples of possible clinical conditions and potential actions to be taken with respect to study drug administration in a given child or group of children. This list is not comprehensive. Consideration of dose changes for each patient will be assessed individually by the treating physician, based on the patient's clinical status and review with the medical monitor.

- Scenario 1: Any study drug-related SAE that results in the death of a single patient

Action: No further dose escalations will take place in any patient; pending evaluation, all other patients will maintain their current dose level and no new patient will be enrolled in the study. A substantial amendment to the Clinical Trial Authorization will be submitted

to the relevant Competent Authorities for approval prior to restarting enrollment and allowing further dose escalations in the event that any study drug-related SAE results in the death of a single patient.

- Scenario 2: One or more study drug-related SAEs in a single patient

Action: If the treating physician, in consultation with the medical monitor, determines that a dose reduction could be expected to reduce the risk of the SAE and not increase the risk of MoCD-related symptoms, the patient may be treated with a lower dose of ORGN001. Subsequent dose escalation for that patient may be considered, based on clinical assessment by the treating physician in consultation with the medical monitor.

- Scenario 3: The same study drug-related SAE occurs in 2 different patients.

Action: In addition to the actions taken under Scenario 2, dosing in subsequent patients may be limited, to achieve concentrations below those observed in the patients with drug-related SAEs, patient to clinical assessment by the treating physician in consultation with the medical monitor.

- Scenario 4: PK exposure in a single patient exceeds the AUC NOAEL limit by greater than 10%

Action: The patient's dose is reduced to a dose level that results in exposure that is below the NOAEL exposure.

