11. PHARMACOKINETICS ASSESSMENTS

Pharmacokinetic assessments will be performed [REDACTED] [REDACTED]. Pharmacokinetic samples also will be collected at Safety Follow-up Visits and any unscheduled dose adjustment visits.

An alternative blood sampling schedule for infants, for whom less blood volume should be collected, must be used [REDACTED] [REDACTED].

Blood samples will be collected for assessment of PK parameters (C_{max} , AUC, $t_{1/2}$). Details of PK sampling time points are specified below. Dosing date, time, amount, precise time of infusion prior to PK sample collection, and exact time of PK sample collection must be recorded in the CRF.

Pharmacokinetic samples will be collected [REDACTED]

: [REDACTED]

- Pre-dose at Day 1 only
- at the EOI ± 5 minutes
- 1 to 2 hours after EOI
- 3 to 4 hours after EOI

If the PK collection kit is not available for Day 1 PK sample collection, samples may be drawn any time from Day 2 to Day 7, when the patient is still in the hospital. In such a case, PK samples should be collected using the following schedule:

- at the EOI ± 5 minutes
- 1 to 2 hours after EOI
- 3 to 4 hours after EOI

Day 1 PK samples will be analyzed and PK assessment completed in time for a scheduled combined SRC/DMC meeting prior to each patient's recommended [REDACTED] dose escalation [REDACTED]

[REDACTED]

[REDACTED]

[REDACTED]

Following recommendation by the SRC for an unscheduled dose adjustment, blood samples will be collected for assessment of PK parameters, as follows:

- On the [REDACTED] day the adjusted dose is administered, the patient will be administered study drug in-clinic, and a blood sample will be collected at the EOI (± 5 minutes), 1 to 2 hours after the EOI, and at 3 to 4 hours after the EOI. The time of infusion, PK

sample collection, the dose administered, and the start and stop time of IV infusion are to be recorded in the CRF. [REDACTED] following an unscheduled dose adjustment, a PK sample will be collected at 1 to 2 hours after EOI.

[REDACTED]

Under no circumstance will the total blood volume obtained exceed the amount considered acceptable for the patient's clinical condition and the institution's guidelines [REDACTED]. If an Investigator decides to deviate from these limits, the deviation must be fully documented, and the Investigator should provide justification for the deviation.

[REDACTED]

[REDACTED]

[REDACTED]

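### Read plainly, the synopsis AUC rule scales the dose by 2 − AUC/midpoint: this is zero at twice the midpoint and, under dose-proportional PK, falls short of the correcting factor midpoint/AUC by the squared relative deviation

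*Combined protocol and SAP*

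**What the plan says.** The rule stands in the Synopsis, under the dose selection strategy, after Table 3. If the Day 1 AUC exceeds the upper limit of the target range, the recommendation is "a decrease by the percentage that the individual AUC is greater than the midpoint of the target AUC range". If it is under the lower limit, the recommendation is "an increase by the percentage that the individual AUC is less than the midpoint of the target AUC range". The range limits are blacked out. The readable text gives no formula, worked example, floor or cap for the rule, and does not name the dose to which the percentage applies. The rule is not repeated in the readable body text.

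Its output feeds a decision for every patient. Section 11 states: "Day 1 PK samples will be analyzed and PK assessment completed in time for a scheduled combined SRC/DMC meeting", ahead of the patient's dose escalation. Section 4.1 places the first adjustment on or before Day 28. Table 3 gives 700 µg/kg/day on Day 1, 1000 at Day 28 and 1200 at Month 3 for term neonates, infants and children, and 525, 900 and 1200 for preterm neonates.

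Several safeguards surround the rule:
- Section 6.1: "the SRC may recommend stopping, increasing, decreasing, or maintaining (current dose) the dose of ORGN001".
- Table 10, footnote b, lists PK sampling among the items of which it says "These assessments will be performed when any dose adjustment occurs".
- Section 2.5: "Doses may be adjusted based on drug-related AEs or changes in clinical parameters, laboratory data, or PK findings".
- Section 6.1.2, Scenario 4, applies when exposure passes the NOAEL AUC by more than 10%: the patient's "dose is reduced to a dose level that results in exposure that is below the NOAEL exposure".

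**The concern.** The rule is tied to the midpoint of the target range, so its evident aim is to bring an out-of-range patient back towards it. A percentage taken relative to the midpoint and then applied to the dose does not do that. A patient 50% above the midpoint needs the dose divided by 1.5, a cut of one third; the sentence cuts it by half. A patient 50% below needs the dose doubled; the sentence adds half. Both errors go the same way, towards too little drug, and they grow with the square of the deviation.

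At stake is the recommendation put to the SRC and DMC before the first dose change. Section 2.2 describes a narrow window for preventing irreversible damage, so a recommendation that is too low has a cost. Scenario 4 in Section 6.1.2 takes the sounder form: it sets the reduced dose by the exposure that the dose will produce.

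**Working it through.** The plan gives no numerical figure to reproduce here; the check is algebra on the two sentences.

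**Inputs.** M is the midpoint of the target range and r = Day 1 AUC / M. Doses are from Table 3. The range limits are redacted, so M and the width of the range are unknown.

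**Step 1: the stated factor.** The percentage above the midpoint is (AUC − M)/M = r − 1; the percentage below is 1 − r.
- Decrease: 1 − (r − 1) = 2 − r.
- Increase: 1 + (1 − r) = 2 − r.

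**Step 2: where it breaks down.** The factor is 0 at r = 2 and negative above it. This needs no PK assumption and holds for any base dose. The decrease rule always applies there: with an arithmetic midpoint and lower limit L > 0, the upper limit is 2M − L, which is below 2M.

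**Step 3: the correcting factor.** Assume dose-proportional PK, which the readable text does not state. Let D be the base dose, D1 the Day 1 dose and c the clearance at adjustment divided by that on Day 1. A dose factor f gives new AUC/M = (D/D1) × r × f / c. Only f = 1/r removes the patient's own deviation, whatever D and c are. The stated factor relative to it is (2 − r)/(1/r) = r(2 − r) = 1 − (1 − r)².

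| r | stated 2 − r | correcting 1/r | stated / correcting |
|---|---|---|---|
| 0.5 | 1.50 | 2.00 | 0.75 |
| 0.7 | 1.30 | 1.43 | 0.91 |
| 0.8 | 1.20 | 1.25 | 0.96 |
| 1.2 | 0.80 | 0.83 | 0.96 |
| 1.3 | 0.70 | 0.77 | 0.91 |
| 1.5 | 0.50 | 0.67 | 0.75 |
| 1.8 | 0.20 | 0.56 | 0.36 |
| 2.0 | 0 | 0.50 | 0 |

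From 700 µg/kg at r = 1.5, the stated rule gives 350 and the proportional rule 467.

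**Step 4: where the new AUC lands.** This depends on D and c.
- Day 1 dose as base, c = 1: new AUC/M = r(2 − r), so 0.96, 0.91 and 0.75 at deviations of 20%, 30% and 50%.
- Scheduled Day 28 dose as base, term, c = 1: (1000/700) × r(2 − r) = 1.37, 1.30 and 1.07 at the same deviations. This is above the midpoint until (1 − r)² = 0.30, a deviation of about 55%. For preterm patients, (900/525) × 0.75 = 1.29 at 50%.
- Day 1 dose as base, clearance up 1.5-fold (assumed): 0.96/1.5 = 0.64, 0.91/1.5 = 0.61 and 0.75/1.5 = 0.50. The proportional factor gives 1/1.5 = 0.67.

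**Step 5: leaving the range.** For an assumed range M(1 ± w), with the Day 1 dose as base and c = 1, the adjusted AUC falls below the lower limit when |1 − r| > √w: 32% at w = 0.10, 45% at w = 0.20, 50% at w = 0.25 and 71% at w = 0.50.

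**Step 6: how often r ≥ 2.** If Day 1 AUC is lognormal with median M (assumed), σ = √ln(1 + CV²) and P(r ≥ 2) = 1 − Φ(ln 2/σ). This gives 0.9%, 3.6% and 7.1% at a CV of 30%, 40% and 50%. The documents give neither the CV nor the median.

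**The case against.** The strongest objection is redaction. Both sentences run into blacked-out text, and there are redactions near the related text in Sections 2.5, 9.5 and 11. A formula or cap could sit there, and what is hidden is not absent from the plan. This stands as a limit on the point. Each redaction within the rule directly follows the mention of the target AUC range, which fits numeric limits better than a formula, but that is an inference.

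The intended percentage may also be relative to the individual AUC. Then 1 − (r − 1)/r = 1/r and 1 + (1 − r)/r = 1/r, and the rule is right. The sentences do not naturally say this, and two readers could still reach 350 or 467 µg/kg for the same patient.

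A reader might infer that the rule always leaves patients below the midpoint. The documents do not support that. The percentage may apply to the scheduled Day 28 dose, in which case Step 4 shows AUCs above the midpoint for most deviations. Clearance also changes: Section 2.5 says that "a function was included to account for the expected impact of renal function maturation" in neonates.

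A reader might also infer that a patient would receive no drug at twice the midpoint. The rule yields a recommendation only, which the SRC and DMC review patient by patient, and PK is sampled again when the dose changes. These safeguards limit the harm but do not correct the rule.

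Finally, a smaller upward step may be deliberate caution in neonates. The readable text gives no such reason, and caution would not explain the steep cut above the range.

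**Conclusion.** The point holds as a minor error in a stated dosing rule. On the plain reading, the zero at r = 2 and the negative values above it follow with no PK assumption. The shortfall against 1/r (4%, 9% and 25% at deviations of 20%, 30% and 50%) needs dose-proportional PK but no choice of base dose. An AUC below the midpoint itself is claimed only for the Day 1 dose with unchanged clearance.

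The effect is small for moderate deviations and large only for big ones. How often those occur cannot be known from the documents, because the range limits are redacted and no between-patient variability is readable. No effect on overall survival is claimed, and nothing in the documents would support one. Confidence is medium, because of the redactions.

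**What to change.** In both sentences, replace the percentage by one instruction: multiply the dose by midpoint AUC / individual AUC. Three additions belong with it:
- Name the dose that is multiplied, and state that an under-exposed patient is not recommended less than the Table 3 dose. Without this, r = 0.8 applied to the Day 1 dose gives 700/0.8 = 875 µg/kg, below the 1000 scheduled for Day 28.
- Cap the result at 1200 µg/kg/day, the top dose in Table 3.
- Check predicted exposure at the time of adjustment in the existing population PK model, with renal maturation, since neither factor accounts for changing clearance.

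Keep the SRC/DMC review and repeat PK sampling as they are. If redacted text already defines the percentage relative to the individual AUC, make the sentences match it; nothing else changes.

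The cost is two sentences in the synopsis, the same edit in the body if the rule is repeated there under redaction, and a model run. No new data or visits are needed. The downside is larger recommended increases at low AUC. With the Day 1 dose as base, r = 0.5 gives 1200 (capped from 1400) instead of 1050 from 700, and 1050 instead of 788 from 525. The cap binds below r = 700/1200 = 0.58 and r = 525/1200 = 0.44. With the scheduled 1000 as base, the cap removes the difference at r = 0.8: 1000 × 1.20 = 1200, and 1000 × 1.25 = 1250 is capped to 1200.

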14.7.3 Secondary Efficacy Analyses	

Section	Description of Change
	
Text added:
 
 “Body weight, length, head circumference, and BMI will be analyzed by converting each parameter to age-adjusted z-scores and age percentiles, and descriptive statistics will be presented to each parameter through Month 12.” “Changes in motor function through Month 12 will be summarized based on data from the administration of the GMFCS-E&R, which is a 5-level classification system that classifies gross motor functional capabilities and limitations as usual performance in the home, school, and community setting.” “The Bayley-III Cognitive and Motor scaled scores and composite scores, as well as percentile ranks, and age equivalents will be summarized through Month 12. Where appropriate, the WPPSI-IV will be used instead of the Bayley-III.” “PEDI standard and scaled scores will be summarized by self-care, mobility, and social function domains through Month 12.”
Appendix B Blood Sampling Volume Tables	
 PK sampling time point blood draws added 1-2 hours after the EOI Total amount of blood drawn per time point adjusted [REDACTED]; total amount of blood drawn per 12-month study period adjusted [REDACTED].

Table 5: Summary of Changes Between Amendment 2 and Amendment 3

Section	Description of Change
Cover page	
 Protocol title updated to reflect addition of infants and children to the study population. (This change has been carried through to all other locations in which the protocol title is shown.) Updated responsible study personnel.
Sponsor Signature Page	
 Updated responsible medical officer. Added additional signatories.
Procedures in Case of Emergency	Updated contact information for reporting SAEs.
2 Synopsis	
 The study period has been adjusted to accommodate long-term follow-up until approval or decision reached on further development of ORGN001, and last patient completion date has been adjusted to 4Q2022. The study background/ rationale, study objectives, endpoints, methodology, inclusion/exclusion criteria, and statistical methods have been updated to reflect the changes detailed in sections below that have been made to expand the study subject population to include older infants and children with MoCD.
2.1 Background	The background has been revised to include information on older children and infants with MoCD.
2.2 Rationale for the Study	Additional text: “Responsibility for the development of ORGN001 in the treatment of MoCD Type A was assumed by Origin Biosciences, Inc, in September 2018.”
2.3 Risk/Benefit Assessment	Additional text: “ In vitro and preclinical studies have identified that ORGN001 has phototoxic potential. Patients and caregivers are instructed to avoid direct sunlight and to use precautions when exposed to the sun. Protective measures include wearing of sunglasses, a hat, long sleeved shirts, long pants and the use of protective sunscreen.”

Section	Description of Change
2.4 Rationale for Patient Population	
Additional text:
 
 “However, the clinical presentation after the neonatal period appears to be more heterogeneous and may progress less rapidly in some patients. In an effort to more fully characterize the potential impact of ORGN001 in MoCD Type A, the study has thus been modified to include infants and children with MoCD Type A, who are treatment-naïve or may have previously received ORGN001 through the early access program (EAP). Infants are defined as those from 29 days to <2 years of age in Amendment 3. Children are defined as those from 2 to 5 years of age (inclusive).” “In infants or children, eligibility will be determined by confirmed genetic diagnosis (genetic confirmation of the diagnosis of MoCD Type A may be obtained after initiation of ORGN001 therapy in certain cases), biochemical profile, and clinical presentation consistent with MoCD Type A.”
2.5 Rationale for Proposed Dosing	
Additional text and tables have been added on the basis of a population PK (PopPK) model:
 
 “Since then, higher doses have been studied and were all well tolerated in rats and dogs using an improved IV formulation. Accordingly, the revised NOAEL values in a [REDACTED] rat study provide a considerable increase in the safety margins [REDACTED].” “The dosing strategy in Table 9 has been simplified compared to the original guidance. This is justified given 1) the much greater safety margin with respect to the NOAEL in the [REDACTED] rat study described above; 2) the excellent safety profile of ORGN001 thus far with all patients tolerating the maximum 1200 µg/kg/day dose and no safety signals identified [REDACTED] [REDACTED]; and 3) the fact that dose increments [REDACTED] were well tolerated in Study ALXN1101-MCD-201.”
2.6 Rationale for Overall Study Design	
Additional text:
 
“Less frequently, older infants and children may present with neurologic symptoms related to MoCD such as seizures, movement disorder, and developmental delay/disability that appears to have a less rapidly evolving course.”

3.1 Objectives	
 Primary objective updated to include infants and pediatric patients who are either treatment-naïve or who have received compassionate use ORGN001. Secondary objectives updated to encompass evaluation of [REDACTED] the effect of ORGN001 on growth and development using age-appropriate assessments, [REDACTED]

[figure not shown]
[figure not shown]
Section	Description of Change
3.2 Endpoints	
Primary efficacy endpoint modified to overall survival. Secondary efficacy endpoints modified to include variables (eg, changes in growth parameters, feeding pattern assessments, and developmental assessments) appropriate to the expanded study subject population and study period.
 
[REDACTED]

4.1 Overall Study Design	
Additional text:
 
 “Infants are defined as those from 29 days to < 2 years. Children are defined as those from 2 years to 5 years (inclusive) at the time of informed consent.” “Eligible patients beyond the neonatal period with genetically confirmed evidence of MoCD Type A, a biochemical profile, and clinical picture consistent with MoCD Type may also be enrolled following completion of Screening/Baseline assessments.” “Data from procedures conducted as part of standard of care prior to study participation may be collected as part of Medical History. Genetic confirmation of the diagnosis of MoCD Type A may be obtained after initiation of ORGN001 therapy in certain cases.” “Due to the rare nature of the disease and no currently available treatment, patients exceeding 36 months of treatment may continue to receive study drug until ORGN001 becomes commercially available or development has stopped. For patients receiving ORGN001 [REDACTED] a safety visit will occur [REDACTED]. Assessments performed during those visits are for the purposes of ongoing safety to receive ORGN001 and may only occur if ORGN001 is not yet commercially available for the patient.” 
[REDACTED]

4.2 Number of Patients	Revised so that no minimum or maximum number of patients is projected for enrollment in the study.

Section	Description of Change
4.3 Study Assessments	
 Updated to include any differences in assessment between neonates, infants, and children [REDACTED] Vital signs assessment [REDACTED] specified as predose (Section 4.3.6). Additional systolic and diastolic blood pressure measurements to be collected [REDACTED] 30 minutes post-EOI was added as a time point. Serum osmolality added as a parameter of blood chemistry/hematology sample analysis to align with the assessment table and CRF (Section 4.3.8). Wechsler Preschool and Primary Scale of Intelligence – Fourth Edition (WPPSI-IV) added as an alternative to the Bayley-III for those patients developmentally beyond the Bayley-III (Section 4.3.12).
5 Schedules of Assessments: (Screening/Baseline and 12-Month Study Period)	
 [REDACTED] WPPSI-IV listed as alternative to the Bayley-III. [REDACTED] Brain ultrasound specified for neonates only. Footnote added that additional systolic and diastolic blood pressure measurements are to be collected [REDACTED] at approximately 30, 60, 90, and 120 minutes post-EOI and at 6 and 12 hours post-EOI.
5 Schedules of Assessments: (Long-Term Treatment Period and Safety Follow Up)	
 WPPSI-IV listed as alternative to the Bayley-III. Safety Follow-up ET Visit column has had developmental assessments added as included and a footnote made stating that these assessments will only occur [REDACTED] for children continuing on ORGN001 past the study follow up period where ORGN001 is not commercially available.
5 Schedules of Assessments: (Following Recommendation by the Safety Review Committee for an Unscheduled Dose Adjustment)	
 PD blood sampling to occur predose. PK blood sampling to occur at EOI (± 5 minutes), 1 to 2 hours after the EOI, and 3 to 4 hours after the EOI.
6.3 Definition of Study End	
Additional text: “Due to the rare nature of the disease and no currently available treatment, patients exceeding 36 months of treatment may continue to receive study drug until ORGN001 becomes commercially available or development has stopped.”

Section	Description of Change
7.2 Patient Inclusion Criteria	
Additional text for the first criterion: “or infant (29 days to < 2 years of age) or child (2 to 5 years of age [inclusive]) with MoCD Type A, previously untreated with ORGN001 or treated with ORGN001 through the EAP”
 
Additional criterion added:
 
 • In infants or children, diagnosis of MoCD Type A, based on: 
 – Confirmed genetic diagnosis (genetic confirmation of the diagnosis of MoCD Type A may be obtained after initiation of ORGN001 therapy in certain cases), biochemical profile, and clinical presentation consistent with MoCD Type A
10 Pharmacodynamics Assessments	
Timing of additional blood and urine sample collection following unscheduled dose adjustments changed to be as follows:
 
On the first day the adjusted dose is administered, the patient will be administered study drug in-clinic, and a pre-dose blood sample will be collected on the first day of the dose adjustment [REDACTED]. A urine sample will be collected at any time during [REDACTED] the dose adjustment visit.

11 Pharmacokinetics Assessments	
 • An additional PK sample was added to occur at 1 to 2 hours after EOI on regularly scheduled collection days, [REDACTED] or on the first day of an unscheduled dose adjustment.
14 Statistical Methods and Planned Analyses	
Added text:
 
 • “Assessments will be binned into analysis visits in such a way that the assessment closest to the target study day among all assessments observed within a window around the target day will be designated for analyses over time. [REDACTED] • “Continuous variables will be summarized using mean, SD, median, minimum, and maximum. Categorical variables will be summarized using percentages and frequency distributions. Confidence intervals will be provided for all means and percentages to aid in interpretation.”
14.1 Determination of Sample Size	Previous section contents deleted; revised to read as follows:

Section	Description of Change
	
“There will be no minimum or maximum number of patients for this study. The final sample size and determination of study success relative to efficacy will depend on the overall survival rate as each successive patient reaches study completion.”

14.2 Analysis Populations	
A Full Analysis Set (FAS) has been defined for performance of the efficacy analyses; the FAS is defined as patients with a confirmed diagnosis of MoCD Type A who have no antenatal and/or postnatal brain imaging prior to initiation of treatment with ORGN001 that indicates cortical or subcortical cystic encephalomalacia or clinically significant intracranial hemorrhage.
 
Additional text: “Additionally, two modified Full Analysis Sets (mFAS) will be used to support the analyses on the FAS:
 
 • Neonate mFAS (NmFAS), [REDACTED] • Pediatric mFAS (PmFAS), [REDACTED] 
[REDACTED]

14.3 Efficacy and Pharmacokinetic Endpoints	
Primary Efficacy Endpoint: Changed to be overall survival.
 
[REDACTED]
 
[REDACTED]
 
 • Changes in growth parameters (height, weight, BMI, head circumference) through Month 12 • Feeding pattern assessments through Month 12 • GMFCS-E&R results through Month 12 • GMFM-88 results through Month 12 
[REDACTED]
 
[REDACTED]
 
[REDACTED]
 
[REDACTED]
 
[REDACTED]

Section	Description of Change
	
[REDACTED]
 
[REDACTED]
 
[REDACTED]
 
[REDACTED]
 
[REDACTED]

14.4 Demographics and Baseline Characteristics	Fas, NmFAS, and PmFAS added.
14.5 Patient Disposition and Extent of Exposure	
Text added:
 
“The number of patients screened, treated, continuing treatment after confirmation of enrollment criteria, and completing the 12-month and 36-month study periods will be tabulated. Reasons for any patient withdrawals will be provided. The number of patients in the safety and efficacy analysis sets, along with reasons for exclusion from analysis sets, will be tabulated.”

14.7 Efficacy Analyses	Fas, NmFAS, and PmFAS added.
14.7.1 Use of Natural History Study ALX-MCD-502	Entire section new (compared to Amendment 2)
14.7.2 Primary Efficacy Analysis	
[REDACTED]
 
“The primary efficacy analysis will summarize overall survival, defined as the interval in months from the date of birth to the date of death or date last known alive (patients still on study will be censored at the data cutoff date), whichever occurs first. The analysis of OS will be based on the Kaplan-Meier methodology for estimation of survival parameters. The median duration of OS will be estimated based on the 50th percentile of the Kaplan-Meier distribution; additional summary statistics, including the 25th and 75th percentiles, 95% confidence intervals (CIs) on the median and the other percentiles and proportion of censored patients. The analysis of OS will be done using the FAS, the NmFAS, and the PmFAS.”

14.7.3 Secondary Efficacy Analyses	
[REDACTED]
 
[REDACTED]
 
[REDACTED]
 
[REDACTED]

Section	Description of Change
	
Text added:
 
 “Body weight, length, head circumference, and BMI will be analyzed by converting each parameter to age-adjusted z-scores and age percentiles, and descriptive statistics will be presented to each parameter through Month 12.” “Changes in motor function through Month 12 will be summarized based on data from the administration of the GMFCS-E&R, which is a 5-level classification system that classifies gross motor functional capabilities and limitations as usual performance in the home, school, and community setting.” “The Bayley-III Cognitive and Motor scaled scores and composite scores, as well as percentile ranks, and age equivalents will be summarized through Month 12. Where appropriate, the WPPSI-IV will be used instead of the Bayley-III.” “PEDI standard and scaled scores will be summarized by self-care, mobility, and social function domains through Month 12.”
	    
14.8.1 Adverse Events	
Text added:

	
“Summaries will include both the number of patients affected and the number of events. For patient counts in summaries by severity or relationship, if a patient has more than one occurrence of an AE for a specific Preferred Term or SOC, the patient will be counted only once in the most extreme category of severity or relationship observed.”

Appendix B Blood Sampling Volume Tables	
Modifications made herein to match time points from the Schedules of Assessments and elsewhere changed within the document:

Section	Description of Change
	
 • PK sampling time point blood draws added 1-2 hours after the EOI [REDACTED] • [REDACTED] • Total amount of blood drawn per time point adjusted [REDACTED]; total amount of blood drawn per 12-month study period adjusted [REDACTED].

Table 6: Summary of Changes Between Amendment 3 and Amendment 4

Section	Description of Change
Administrative	Updates to table numbers throughout the protocol to account for additional summary of changes table for protocol amendment 4 [REDACTED] [REDACTED]
4.3.7	Electrocardiograms will be collected for each patient at Screening/Baseline when feasible, [REDACTED] [REDACTED] and at any Safety Follow-up Visit, and at the Early Termination Visit, if applicable, or as per SRC recommendation.
